## 11.1 Figure 1: Overview of Study Visit Process

The CI/RN or designee will observe the subject using purpleDx and will use a simple tick-box Likert scale to answer a series of five questions about their ability to use the device. Each subject will also be asked to answer the same five questions using the simple tick-box scale to rate their ease of using the app (see Appendix 8 Section A – Device Setup and Use).

The CI/RN or designee will answer 3 additional questions (see Appendix 8 Section B – Time and Workflow).

Lastly, the CI/RN or designee and each subject will be asked to complete two open feedback questions to provide details of any difficulties or issues encountered during the process for setup, performing the scan, obtaining and recording results (see Appendix 8 Section C – Open Feedback).

All responses and required study information will be recorded in each subject's medical records or agreed form of source documentation. Data from purpleDx will be automatically uploaded to the Sponsor's database in the cloud. This information will only be identifiable by the subject study number i.e. no Patient Identifiable Data (PID) will be included.

Upon completion of the subject's visit, the CI/RN or designee will transcribe the information from any source documentation into the electronic Case Record Form (eCRF) within pre-agreed timelines (e.g. within 1 week of the date of the study timepoint).

The source documentation will be made available for external monitoring to ensure accuracy and validity of data transcribed into the eCRF.

All source documentation and the ISF must be kept for at least 10 years after the device is last placed on the market to comply with the medical device marketing requirements of regulators following completion of the study. Archival processes will be agreed between CUH and the Sponsor as part of the negotiation process to establish the Clinical Trial Agreement and ensure access can be arranged if required in future for auditing purposes.

The Sponsor will provide a secure database to act as the eCRF for the study raw data. Access to the eCRF will be password protected, and no patient identifiable data will be held within the eCRF. Each subject will only be identifiable by subject study number.

To access the eCRF, each user will require access rights to be granted by the Sponsor.

## 11.2 Definition of End of Study

The end of this study is defined as the 30 days after the date when the last recruited participant has completed the study testing procedures i.e. the last data point has been collected for the last study participant (30-day mortality status).

## 12.0 SUBJECT ELIGIBILITY CRITERIA

#### 12.1 Inclusion Criteria

- 1) Sex at birth classified as male or female
- 2) 18 years of age and above, presenting to CUH Emergency Department
- 3) Able to read and understand the patient information sheet in English
- 4) Capacity and ability to sign an informed consent form
- 5) With or without respiratory or cardiorespiratory symptom/s

#### 12.2 Exclusion Criteria

- 1) Unable to sit up i.e. cannot lie completely flat (supine)
- 2) Known pregnancy in women of child-bearing potential (WOCBP)
- 3) Unable to comply with the requirements of the investigation in any way
- 4) Prisoners or young offenders

#### 13.0 STUDY PROCEDURES

#### 13.1 Patient Screening and Recruitment

The RN or designee will approach potential subjects in the waiting area of the CUH Emergency Department to determine their interest in participating in the study. Subjects will be given a Patient Information Sheet (PIS) and Informed Consent Form (ICF), to read and consider and will be given sufficient time to ask any questions and receive satisfactory explanation to enable them to decide whether they want to take part.

Subjects will confirm their willingness to participate in the study by signing the study-specific ICF in the presence of the CI/designee. The original signed ICF will be scanned into the subject's electronic patient record then placed in the relevant section of the Investigator Site File (ISF). A photocopy of the signed ICF will be given to the subject. The subject will be assigned a unique anonymised study number. Signing the ICF and assignment of a study number constitutes recruitment into the study.

#### 13.2 Informed Consent Process

Informed consent must be obtained prior to the participant undergoing any activities that are specifically for the purposes of the study.

Subjects will be approached in the CUH Emergency Department to determine interest in participating in the study. Subjects will be given sufficient time to read the PIS, receive answers to any questions they may have, and to consider whether they want to take part.

Subjects will confirm their willingness to participate in the study by signing the study-specific ICF. The original signed ICF will be placed in the ISF, and a photocopy will be filed in the subject's medical record and a photocopy will also be given to the subject.

This study requires participants to be capable of providing consent to take part and therefore a legal representative will not be able to sign consent on behalf of a subject. The assessment of capacity to consent involves consideration of whether the subject can understand the following points:

- the purpose and nature of the study
- what the study involves
- any risks and/or benefits of the study
- participation is voluntary
- decision whether to participate will not affect the subject's healthcare in any way.

The PIS and ICF will be printed on CUH headed paper and will have been approved by a Research Ethics Committee suitable for the assessment of medical device studies prior to the start of the study. Subjects will have the opportunity to ask any questions of the CI/RN to help them decide if they want to take part in the study.

#### 13.3 Withdrawal of Consent

Subjects can withdraw their consent to participate in this study at any time and without affecting their subsequent clinical care in any way. This will be explained to the subject during the informed consent process.

If a subject withdraws consent to participate in the study after signing the ICF but prior to undergoing any study procedures, all study-related documentation will be destroyed. The subject will not be allocated a study number. No study information will be recorded. No study procedures will be undertaken.

If a subject signs the ICF, is allocated a study number and at least begins the measurement of any of the physiological parameters being investigated in the study but changes their mind and withdraws consent, the information will be kept as part of

the subject's medical record to maintain complete transparency but will not be included in the analysis in any way. The subject will still be asked to rate their ease of using the app but has the right to refuse. Their reason for withdrawal of consent will be ascertained as far as possible to determine if it was in any way due to using purpleDx.

#### 13.4 Randomisation

This is not applicable to this clinical trial as all subjects undergo the same testing process and are not assigned to treatment arms. Each subject will act their own control, by being tested with standard clinical equipment and the SaMD.

#### 13.5 Schedule of Events

## 13.5.1 Per-participant Activities

Activity	To be done at ED Visit
Review of PIS and signing ICF	Х
Height	Х
Weight	Х
Chest circumference	Х
Smoking status (number of pack years for smoker)	Х
Relevant medical conditions (including confirmation of no known pregnancy in WOCBP)	х
Angle of recline (if subject is lying on bed/trolley)	x
Measurement of skin tone	Х
Measurement of light level	Х
Measurement of PEF, FEV 1 , RR + HR using purpleDx ^	Х
Measurement of PEF, FEV 1 , RR + HR using standard equipment/means* ^	х
Completion of usability questions	Х
Adverse event information	Х

\*standard equipment for PEF and FEV1 is the Vitalograph spirometer and for HR is the Nonin pulse oximeter and standard means for RR is manual count by visual inspection

^ each parameter will be measured three times.

## 13.5.2 General Study Activities

Activity	Team Member	Estimated Time to complete activity per enrolled subject
Taking informed consent	CI/RN	15 minutes
Completion of visit assessments and source documentation	CI/RN/designee	45 minutes
Input of data into each subject's eCRF and CI sign off	CI/RN/designee	15 minutes
Maintenance of Investigator Site File and Essential Documentation	CI/RN/designee	30 minutes
Query resolution (arising from SDV)	CI/RN/designee	30 minutes

#### 14.0 STATISTICAL ANALYSIS PLAN

The Statistical Analysis Plan (SAP) incorporates testing for peak expiratory flow (PEF) and forced expiratory volume in one second (FEV1), heart rate (HR) and respiratory rate (RR) using the new device (PurpleDx), compared to these standard clinical measures using the Vitalograph spirometer, manual respiratory count and pulse oximeter in a single-visit A&E setting. The statistical approach evaluates agreement and usability for all four parameters.

## 14.1 Study Objectives

## 14.1.1 Primary Objective

• To evaluate agreement between the new device and standard clinical measures for assessment of Peak Expiratory Flow; PEF (Primary Endpoint).

## 14.1.2 Secondary Objectives

- To evaluate the agreement between the new device and reference methods for assessment of:
  - Forced Expiratory Volume in one second; FEV1
  - Respiratory Rate; RR
  - Heart Rate; HR.
- To assess the **usability** of the new device for patients and clinicians.

#### 14.2 Data Collection

• Participants: Adults (≥18 years) presenting to the ED with or without respiratory or cardiorespiratory symptoms.

#### Procedure:

- o Three measurements of PEF, FEV1 using the new device and reference method (best effort recorded).
- o Three measurements of HR and RR using the new device and standard clinical devices/means (average recorded).
- Usability questionnaires (Likert scales) completed by patients and clinician post-use.

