## 7.2 The Investigational Medical Device

The medical device under investigation in this study is a smartphone application (app), called purpleDx which has been developed by electronRx Ltd. It will be used to assess peak expiratory flow (PEF), forced expiratory volume in one second (FEV1), respiratory rate (RR) and heart rate (HR) by a non-contact scan utilising the phone's camera function. According to the classification of Medical Devices by the Medicines and Healthcare products Regulatory Agency (MHRA) in the UK and the Medical Device Regulation in Europe (MDR EU), the app should be classified as Class IIA Software as a Medical Device (SaMD) and is currently pending approval for clinical use. Class IIA is medium risk as it has the potential to be used to inform changes to treatment regime if the app was further developed for such purposes.

The purpleDx app is designed to be easy to use, with two non-contact scans captured over the course of just one minute each. The subject should ideally sit on a chair in a

relaxed, upright position, preferably with their back against the chair. Alternatively, the subject may recline on a bed or trolley, with a note made of the corresponding angle of recline. The smartphone must be immobilised by using a phone stand or by being propped against a sturdy object. The phone should be perpendicular to the subject. The first one-minute scan is to determine Breath Scan namely Peak Expiratory Flow (PEF), Forced Expiratory Volume in One Second (FEV1), and Respiratory Rate (RR), employing reference markers affixed to the subject's hands (one on each hand) to aid with visual tracking. The second one-minute scan is a Pulse Scan to measure Heart Rate (HR).

For PEF, FEV1 and RR, the subject presses 'Breath Scan' on the smartphone and must then adjust their camera image profile on the screen according to the on-screen instructions. Once the image is correctly aligned, the recording starts automatically. A countdown of the sixty-second recording period will be displayed on the screen during the scan. The app will save the scan results to the cloud for analysis. The Breath Scan will be carried out 3 times. When the automatic analysis from the 3 Breath Scans is complete, the PEF, FEV1 and RR results will be displayed on a results screen.

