For HR, the subject presses 'Pulse Scan' and follows the on-screen instructions to position their face to fit the oval shown on the screen. Once the face is correctly positioned, the app will automatically start the recording. A countdown of the sixty-second recording period will be displayed on the screen during the scan. The HR results will appear after each Pulse Scan has been performed.

Screenshots of the various app screens are shown in Appendix 2.

Although not done as part of this clinical protocol, data could potentially be collated over time as the patient performed sequential testing.

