The subject will use the purpleDx device to perform the Breath Scan to measure PEF, FEV1 and RR three times. Concurrently, the CI/RN or designee will observe the subject and count the number of breaths taken during each Breath Scan and will record the results on the source document. The CI/RN will use the standard Vitalograph spirometer equipment to obtain three sets of measurements for PEF and FEV1. The subject will then use the Pulse Scan on the new device to obtain three HR readings. A standard pulse oximeter will be used concurrently to obtain three HR results. Thus, three sets of results will be produced for PEF, FEV1, RR and HR by both the standard means and by the investigational equipment. Appendices 1 and 2 provide a detailed overview of the process and the app screenshots. For details of the equipment being used in the study, see Appendix 6. The purpleDx results will be displayed on the smartphone screen. The CI/RN or designee will copy the results from the new device and the standard equipment onto the subject's paper visit records to act as the source document for the parameter values. A PDF file will subsequently be emailed to the CI/RN or designated member of the clinical study team to verify the handwritten source document results from the purpleDx Breath Scan.

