## 20.3.7 Results Screen for Breath Scan (PEF, FEV₁ and RR)

The three sets of results for PEF, FEV1 and RR will appear on the Results screen within 2 to 3 minutes of the measurements being taken, depending on the speed of the internet connection.

If any of the three sets of measurements have been unsuccessful and there are missing results, the CI/RN should ask the subject to repeat the Breath Scan. If there are any obvious reasons as to why the scan did not work, these will be noted by the CI/RN along with the need to perform a repeat scan. When the scan has been repeated, the results screen with be updated to include all successful measurements on the same screen.

A maximum of 3 retry Breath Scans should be attempted as needed to produce 3 results for each of the 3 parameters PEF, FEV1 and RR. If there are still missing data after 3 retry Breath Scans have been carried out, the missing results will be recorded as 'Not Available' (NA). The number of additional scans needed will be recorded.

Confirmation of the results for PEF, FEV1 and RR will subsequently be sent to the CI/RN as a PDF document for filing in the subject's medical notes to enable verification.

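### HR and RR agreement is computed on three-scan averages, so the limits of agreement will be narrower than those for a single reading; the plan should analyse the scan-level pairs or confine its claim to the average

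*Protocol*

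**What the plan says.** **What is analysed.** Protocol section 14.2 (Procedure) has "Three measurements of HR and RR using the new device and standard clinical devices/means (average recorded"). Section 14.3.2 then judges each subject's pair of values against the tolerance and reports the proportion of subjects who succeed. Section 14.4.1 counts one paired result per subject. The estimand table (14.10) gives mean bias, 95% limits of agreement and the percentage within ±10% as the HR and RR summary measures. All of these are therefore computed on three-scan means.

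**What is collected.** Section 11.0 has the observer "count the number of breaths taken during each Breath Scan". For HR it says "A standard pulse oximeter will be used concurrently to obtain three HR results". Three concurrent device/reference pairs per subject exist for each parameter.

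**What the app shows.** For HR, section 7.2 says "The HR results will appear after each Pulse Scan has been performed", and section 20.3.8 agrees. For RR, section 20.3.7 says "The three sets of results for PEF, FEV 1 and RR will appear on the Results screen within 2 to 3 minutes". Section 7.2 describes use of the app "with two non-contact scans captured over the course of just one minute each", but also says of the Breath Scan: "When the automatic analysis from the 3 Breath Scans is complete, the PEF, FEV 1 and RR results will be displayed on a results screen".

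**What is not stated.** The text does not say that the app outputs a mean of three scans, that HR and RR performance is claimed only for such a mean, or that the limits will be adjusted for averaging.

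**The concern.** Averaging three readings per method removes up to two thirds of the scan-to-scan part of the variance before agreement is assessed. The resulting limits describe the difference between two three-scan means, which is not the quantity a user reads after one Pulse Scan.

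The protocol expects scan-to-scan disturbance. Section 11.0 records movement, talking and coughing during each measurement, and section 14.10 lists talking and movement artefact as intercurrent events for RR and HR.

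At stake is how the HR and RR results are described. Section 14.4.3 wants the study to support a quotable performance figure, and section 14.10 interprets HR agreement as adequate for triage and monitoring. A figure earned on three-scan means could be read as applying to one reading.

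**Working it through.** **1. The plan's own figures.** Section 14.4.2 (carried to HR and RR by 14.4.3) uses n = 150, p1 = 0.95 and two-sided α = 0.05:

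power = Φ{[(p1 − p0)√n − 1.96√(p0(1 − p0))] / √(p1(1 − p1))}

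For p0 = 0.85, 0.88, 0.89 and 0.90 this gives 99.2%, 84.4%, 71.2% and 54.5%, against the printed 99%, 84%, 71% and 54%. The table reproduces and is not in dispute. What matters is which quantity its 95% refers to.

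**2. Effect of averaging on the limits.** Let the device-minus-reference difference on one scan have between-subject variance B and scan-to-scan variance W, with scan errors independent within a subject.

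- Single scan: variance B + W
- Mean of three concurrent pairs: variance B + W/3
- With w = W/(B + W), SD ratio (mean/single) = sqrt(1 − 2w/3)

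The ratio runs from 1 (w = 0) to 0.577 (w = 1), so the limits are 0 to 42% narrower. Mean bias is the same either way. The documents do not give w, so it is varied as an assumption.

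**3. Effect on the percentage within ±10%.** Assume normal differences, zero bias, and 95% of three-scan means within ±10%. Then the single-reading proportion is 2Φ(1.96 × ratio) − 1. The last column is the exact binomial probability, at n = 150, that the Wilson lower bound reaches 80% (the HR/RR rule in 14.4.3, which needs at least 130 of 150 successes) when one reading per subject is analysed.

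| w | SD ratio | Single limits ÷ averaged limits | Single readings within ±10% | Chance lower bound ≥ 80% |
|---|---|---|---|---|
| 0 | 1.000 | 1.00 | 95.0% | >99.9% |
| 0.25 | 0.913 | 1.10 | 92.6% | 99.7% |
| 0.5 | 0.816 | 1.22 | 89.0% | 85.6% |
| 0.75 | 0.707 | 1.41 | 83.4% | 16.9% |
| 1 | 0.577 | 1.73 | 74.2% | about 0% |

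**4. The same in beats per minute.** Assume HR 80 (±10% is ±8 bpm), zero bias and a single-scan difference SD of 5 bpm. For single readings, 2Φ(8/5) − 1 = 89.0% are within tolerance, with limits ±9.8 bpm (1.96 × 5). For three-scan means the SD is 5 × sqrt(1 − 2w/3):

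| w | SD of mean difference | Limits (bpm) | Within ±8 bpm |
|---|---|---|---|
| 1 | 2.89 | ±5.7 | 99.4% |
| 0.75 | 3.54 | ±6.9 | 97.6% |
| 0.5 | 4.08 | ±8.0 | 95.0% |
| 0.25 | 4.56 | ±8.9 | 92.0% |
| 0.1 | 4.83 | ±9.5 | 90.2% |

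**5. Dependence on bias.** With bias inside the band, averaging still raises the proportion. At HR 75 (band ±7.5), bias 5 and SD 4, it is 73% for single readings, 78% for means at w = 0.5 and 86% at w = 1. With bias outside the band, it lowers it. At RR 15 (band ±1.5), bias 2 (the edge of the RR bias target in 14.3.5) and SD 1, it is 31% for single readings, 27% at w = 0.5 and 19% at w = 1.

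**The case against.** **RR.** Section 7.2 says the Breath Scan is carried out three times and shows RR once all three are analysed. A three-scan summary is a defensible unit there. This stands, and it makes the RR case weaker than the HR case. It does not remove it, because section 20.3.7 still presents separate values and section 7.2 also speaks of one-minute scans.

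**Missing screens.** The results screenshots are not reproduced in the text, so a displayed mean cannot be ruled out. That is fair. The finding rests on the text, which mentions none.

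**Size.** It depends wholly on assumed inputs. Skin tone, light level and obstructions, all recorded under section 11.0, act at subject or visit level and could make w small. At w = 0.1 the gap in step 4 is 90.2% against 89.0%. This stands.

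**Reach.** Averaging is openly specified and applied to both methods, it reduces noise in the manual count, and it concerns secondary endpoints only. All true. It remains a different quantity from a single reading.

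**Readings that go too far.** A reader might infer that the device could meet its target on means and miss it on every reading a clinician sees. That does not follow: in step 4, 89.0% of single readings are within tolerance. Nor does the HR/RR verdict necessarily change. The ≥95% figure in 14.3.5 is expected performance, while the stated rule in 14.4.3 is a lower bound of at least 80%, which 150 single readings at 89.0% would meet with about 85% probability. Nor is the percentage within ±10% always flattered, as the RR example in step 5 shows.

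**Conclusion.** The point holds, as a should-fix matter on secondary endpoints. Limits of agreement on three-scan means are narrower than single-reading limits whenever there is any scan-to-scan error, at any bias, by 0 to 42%. The percentage within ±10% will usually be higher as well, on condition that the mean bias lies inside the band.

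The direction for the limits follows from the algebra, given independent scan errors. The size is unknown because no within-subject SD is given, so the tables above are illustrations resting on assumed normality, bias and w. The documents do not support a claim that the HR or RR conclusion is wrong, nor that RR is affected as clearly as HR. Mean bias, the printed power table and the primary PEF endpoint are untouched.

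**What to change.** For HR and RR, make the concurrent scan-level pairs the basis of the analysis:

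- Bland-Altman limits for replicated paired data, from a model with a subject effect and using the total SD of a single-scan difference.
- A per-scan proportion within ±10%, with a confidence interval clustered on subject.
- The three-scan mean kept as a labelled secondary summary, using only scans that have both a device and a reference value. Sections 20.3.7 and 20.3.8 allow individual device results to be unavailable, and section 14.2 does not tie the two averages to the same scans.

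If a three-scan average is the intended output, the protocol should say so and restrict the HR and RR performance claim to it.

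The cost is a change of analysis wording. Section 11.0 already has three results per method recorded for each parameter, so no further subjects or procedures are needed. The downside is that the HR and RR figures may look less favourable.
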